online Unified Protocol). This session homework assignment data will also be downloaded to Yale's Secure Box drive upon retrieval from the Karolinska Institutet server; it will also remain on the Karolinska Institutet server after transfer to Yale. Participant session notes will be stored on Yale's Secure Box. Participant tracking and scheduling data will be recorded on a study database stored on Yale's Secure Box. One password-protected linking database containing participant names and ID codes will be kept on Yale's Secure Box and accessible only by study staff.

Yale's secure Qualtrics server meets recognized security standards for storing participant data. The Karolinska Institutet's secure server used in several prior and current trials of internet-based CBT also meets recognized security standards for storing participant data. Details about the security of this server have been submitted in conjunction with this protocol and include intensive physical and digital system access control and data separation control.

Participants will be identified with participant ID number, not with participant name.

All study computers will be encrypted and password protected. Online surveys (yale.qualtrics.com) will use an encrypted web service (https) and will not ask participants' name or other identifying information, only participant ID number. The linking database will be kept separate from study data and will be password protected.

5. How will	l the digital data be st	ored? 🗌 CD 🗌	DVD 🖂 Fl	lash Drive	Portable	Hard
Drive	Secured Server	Laptop Cor	nputer 🖂	Desktop Con	nputer	Audiotaping
Videotap	oing Handwritten ne	otes 🗌 Other				

6. If applicable, how will transfer of data to Yale be completed? See http://its.yale.edu/secure-computing/protecting-yales-data/data-and-information-classification-yale-university

Session homework data will be transferred from the the Karolinska Institutet to Yale using the HIPAA-compliant Yale Secure Box. This homework data will not contain participant identifying information; only study ID.

7. What will be done with the data when the research is completed? Are there plans to destroy the identifiable data or the link to personal identifiers? If yes, describe how, by whom and when identifiers will be destroyed. If no, describe how the data and/or identifiers will be secured.

After study completion, data will be stored on an encrypted, password-protected server at the Yale School of Public Health. The identifiable data will remain separate from the remainder of participant data. After three years of study completion, the link to personal identifiers will be destroyed.

Deidentified audio recordings, labeled only with study IDs, will be transcribed using GoTranscript, a confidential external transcription service. GoTranscript protects audio files with 2048-bit SSL encryption. Audio files for transcription are cut into 5-10 minute chunks and transcribed by different transcriptionists who have each signed non-disclosure agreements. Audio files are deleted from GoTranscript servers upon transcript completion and will then be uploaded by study staff to

Yale's Secure Box folder. After three years from study completion, audio transcripts will be destroyed.

8. Will a Certificate of Confidentiality be needed? (*See also the NIH Certificate of Confidentiality Kiosk, http://grants.nih.gov/grants/policy/coc/index.htm*)

We will request an NIH Certificate of Confidentiality for the full randomized control trial.

SECTION VII: POTENTIAL RISKS AND BENEFITS

9. **Risks:** Describe the reasonably foreseeable risks, including risks to participant privacy, discomforts, or inconveniences associated with participants participating in the research. *Note: All studies have the potential for risk, if not physical, there may be psychological, reputational, or financial risks or risks to breach of confidentiality*

Study participants are at minimal risk for harm as a result of participation in the proposed research study. Although unlikely, one risk of the proposed study is that participants will experience emotional discomfort as a result of completing the quantitative assessments, intervention, and phone interviews. Breach of participants' confidentiality presents another possible risk. The investigative team's strategies to protect against both risks are described below.

10. Minimizing Risks: Describe the manner in which the above-mentioned risks will be minimized.

Recruitment and Informed Consent: The investigative team has conducted a number of studies involving LGBTQ young adults, which have involved asking participants to complete potentially sensitive interviews and self-report measures. Thus, we have extensive protocols in place for all aspects of the study. All staff complete IRB (re)certification as required. All new staff and research volunteers will receive training in issues pertinent to research among LGBTQ young adults, and will sign a confidentiality pledge prior to any contact with participants or data. No identifying information is collected prior to the moment at which a participant provides informed consent.

Participants will be recruited into the study by online advertisements, emails, or flyers containing a link to our brief screening instrument online. Participants who pass the online screening instrument will be called by a research assistant. Before completing phone screening questions, participants will be provide verbal consent specific to the screening.

At the end of the phone screening, research assistants will e-mail eligible participants a PDF copy of the consent form and review the consent document with them. The RA will ensure that the participant understands the risks associated with the disclosure of information that could indicate imminent threat to self or others. Verification of comprehension of informed consent will be accomplished by asking participants to recall central points in the consent process; points of confusion will be clarified. Once participants have fully understood the consent, they will be asked to provide verbal consent. RAs will be instructed to contact the PI or project coordinator if he or she is unsure about any participant's capacity to consent.

Page 16 of 22

Protection Against Emotional Discomfort. It is possible that participants may experience emotional discomfort in responding to assessments or session material. While every possible step will be taken to minimize such risk, consent documentation will make it clear that if participants have any concerns about any aspect of the study they may refuse to continue with the study at any time, without penalty. In addition, we will remind participants during the course of their assessments that they can refuse to answer any questions and may discontinue participation at any time. Staff members at our lab will be thoroughly trained in appropriate responses to participant distress through tri-annual trainings by a licensed clinical psychologist. This training will address the appropriate handling of imminent threats and provision of referrals to counseling services in less imminent clinical situations. We have developed protocols for mitigating such risks as employed in our other and in-person online treatment studies with LGBTQ young adults. One such study recently took place in rural Appalachian Tennessee with no adverse events (Protocol # 1512016952).

Protection Against Breach of Confidentiality. The primary potential risk to participants is breach of confidentiality. Breaches of confidentiality will occur if a participant reports a clear intention to harm himself or another person. Additionally, health care professionals are required by state law to report suspected cases of abuse or neglect. The likelihood that any additional breaches of confidentiality would occur is minimal, as steps will be taken to guard against this risk. To protect participants' confidentiality, we will obtain a Federal Certificate of Confidentiality. All study therapists and research assistants will undergo rigorous training in maintaining participants' privacy and confidentiality and will be in possession of valid Collaborative Institutional Training Initiative (CITI) certificates. Further, immediately upon providing consent, all participants will be assigned an identification number, which will only be kept on an electronic database that will be password protected and located on a designated study computer. This information will not be stored with any other data and no other identifying information will appear on any form. All contact with participants will be made by therapists and research staff under explicit guidelines to preserve confidentiality when telephoning, emailing, or mailing information to participants. All materials with identifying information will be kept in one password protected electronic file on Yale Secure Box. Participants will provide alternative contact information (email, phone numbers, and mailing address) for compensation and study retention purposes. This information will be treated in the same confidential manner as all participant information, as described here.

11. Data and Safety Monitoring Plan: All studies require the inclusion of a Data and Safety Monitoring Plan (DSMP) with an explicit statement of overall risks (e.g., minimal, greater than minimal/moderate, or high), a means to address attribution and grading of adverse events and a description of procedures for monitoring the ongoing progress of the research and reporting adverse events. The Data and Safety Monitoring Plan should describe how the principal investigator intends to provide ongoing supervision and evaluation of the activities of the study including whether appropriate progress is being made. It should document the procedures and means to protect the welfare and safety of subjects and protect the integrity of the data.

The plan must include provisions for data review and performance of safety reviews, at a specified frequency, as well as the plan for reporting to the HSC and/or other internal or external organizations. When participating in a multi-site study, the Yale principal investigator must indicate how safety reports and/or reporting of serious adverse events from other sites will be provided to the Yale HSC.

Include an appropriate Data and Safety Monitoring Plan (DSMP) based on the investigator's risk assessment stated below. (Note: the HSC will make the final determination of the risk to subjects.).

12. What is your assessment of the overall risk level for subjects participating in this study?

minimal

13. If children are involved, what is your assessment of the overall risk level for the children participating in this study?

minimal

- c. Copy, paste, and then tailor an appropriate Data and Safety Monitoring Plan from http://www.yale.edu/hrpp/forms-templates/biomedical.html for
 - i. Minimal risk
 - ii. Greater than minimal/moderate risk
 - iii. High

The principal investigator is responsible for monitoring the data, assuring protocol compliance, and conducting the safety reviews quarterly. During the review process the principal investigator will evaluate whether the study should continue unchanged, require modification/amendment, or close to enrollment.

The principal investigator, the Institutional Review Board (IRB) or the Data Safety Monitoring Board (DSMB) have the authority to stop or suspend the study or require modifications.

This protocol presents minimal risks to the subjects and Unanticipated Problems Involving Risks to Subjects or Others (UPIRSOS), including adverse events, are not anticipated. In the unlikely event that such events occur, Reportable Events (which are events that are serious or life-threatening and unanticipated (or anticipated but occurring with a greater frequency than expected) and possibly, probably, or definitely related) or Unanticipated Problems Involving Risks to Subjects or Others that may require a temporary or permanent interruption of study activities will be reported immediately (if possible), followed by a written report within 5 calendar days of the Principal Investigator becoming aware of the event to the IRB (using the appropriate forms from the website) and any appropriate funding and regulatory agencies. The investigator will apprise fellow investigators and study personnel of all UPIRSOs and adverse events that occur during the conduct of this research project (e.g., through regular study meetings, via email as they are reviewed by the principal investigator.) The protocol's DSMB will be informed of serious or unanticipated adverse events within 5 days of the event becoming known to the principal investigator.

14. For multi-site studies for which the Yale PI serves as the lead investigator:

- i. How will adverse events and unanticipated problems involving risks to subjects or others be reported, reviewed and managed?
- ii. What provisions are in place for management of interim results?
- iii. What will the multi-site process be for protocol modifications?

Yale University is the only site at which participants will be enrolled.

Page 18 of 22

15. Potential Benefits: Identify any benefits that may be reasonably expected to result from the research, either to the participant(s) or to society at large. (*Payment of participants is not considered a benefit in this context of the risk benefit assessment.*)

Mental health problems and associated behavioral health risks (e.g., substance abuse, suicidality, sexual risk) among LGBTQ young adults is a clear public health concern in need of easy-todisseminate solutions. All participants in the present study will be exposed to information about mental and behavioral health in relation to social stress. We anticipate that participants will acquire knowledge and skills and will receive support needed to improve their capacity for managing mental and behavioral health risk. Benefits to society in general are anticipated through the dissemination of intervention findings and community trainings in the EQuIP treatment approach. Results will better inform local and national public health agencies about potentially effective outreach and prevention strategies that can be delivered to LGBTQ young adults who experience stress-sensitive mental health disorders, such as depression and anxiety, and related behavioral risks. In sum, the potential benefits outweigh the potential risks to subjects.

We propose to further test a preliminarily efficacious intervention, this time online, to help LGBTQ young adults manage their mental and behavioral health. Findings from this study can be used to help guide prevention efforts for both LGBTQ young adults and other socially disadvantaged groups who experience stress-sensitive mental health disorders. Given the public health importance addressed by this project and the potential benefit of the information to be gained, we believe that the risk to subjects is reasonable. Further, the information from this intervention can serve to benefit more widespread mental health promotion efforts. Specifically, information from this study will inform public health agencies regarding the effectiveness of an intervention that addresses co-occurring mental and behavioral health risks. This test will lay the groundwork for future studies examining the strategic implementation of this intervention.

SECTION VIII: RESEARCH ALTERNATIVES AND ECONOMIC CONSIDERATIONS

1. Alternatives: What other alternatives, if any, are available to the study participants outside of the research?

All participants and potential participants will be provided with a list of community referrals, including, as available in each participants' region, psychological, medical, HIV/STD testing, substance use, and housing supports. Notably, we intentionally recruit participants from low-resources regions as a matter of the capacity of our intervention to serve as a needed public health response.

2. **Payments for Participation (Economic Considerations):** Describe any payments that will be made to participants, if any, the amount and timing of payments and the conditions for receiving this compensation (if applicable). If you plan to hold a drawing, be sure to include the following on any consent or recruitment materials mentioning the sweepstakes: 1) the value of the prize; 2) the sponsor of the prize (this cannot be a federal funding source); 3) the odds of winning; 4) that there are no restrictions to winning.

Participants will receive \$30 for completing the baseline assessments, \$30 for completing the 3month follow-up assessments, \$10 for each weekly session or mood tracking survey completed, and \$30 for completing the 6-month follow-up assessment (total = \$190). Payment will be prorated for partial study completion (i.e., participants will only be paid for the parts of the study that they completed). Participants who participate in the phone interview will receive \$30. All study payments will be in the form of e-mailed Amazon gift cards or Venmo payments. Venmo payments will be sent to participants from the private @Yale-Study account and will be accompanied with the text "Thank you for your time."

Starting in September 2021, as participants start to become eligble to complete their final follow-up assessments, we will hold a monthly sweepstakes for all randomized participants who successfully completed their 8-month follow-up assessment in the past month. Each month, the sweepstakes winner will be selected using a random number generator. Winners will receive \$100 via Amazon gift cards or Venmo payments (as per their indicated preference) and will be notified via email directly after the selection of the sweepstakes winner. We will hold this monthly sweepstakes each month from September 2021 until February 2022, when the last randomized participant will have completed their final follow-up assessment.

All randomized participants will be notified about the sweepstakes via email in September 2021, including the sweepstakes prize, frequency of sweepstakes and odds of winning. Following that, participants will be notified about the monthly sweepstakes in their follow-up reminder emails from the EQuIP research team.

For participants who have previously completed their 8-month follow-up assessment (i.e., a total of 10 participants as of 8/26/21), we will hold a retrospective sweepstakes in order for these participants to have the same opportunity of receiving \$100. In the same way as described above, these participants will be notified via email about the sweepstakes. We will hold this one-time retrospective sweepstakes at the beginning of September 2021.

3. **Costs for Participation (Economic Considerations):** Clearly describe the participant's costs associated with participation in the research, if any, and the interventions or procedures of the study that will be provided at no cost to participants.

Study participation will generate no cost for participants. All study treatment (online EQuIP, online Unified Protocol) will be provided free of charge to all study participants.

SECTION IX: PRINCIPAL INVESTIGATOR AGREEMENT

As the principal investigator of this research project, I certify that:

- 1. The information provided in this application is complete and accurate.
- 2. I assume full responsibility for the protection of human participants and the proper conduct of the research.
- 3. Subject safety will be of paramount concern, and every effort will be made to protect participants' rights and welfare.
- 4. The research will be performed according to ethical principles and in compliance with all federal, State and local laws, as well as institutional regulations and policies regarding the protection of human participants.
- 5. All members of the research team will be kept apprised of research goals.
- 6. I will obtain approval for this research study and any subsequent revisions prior to my initiating the study or any change and I will obtain continuing approval of this study prior to the expiration date of any approval period or submit a request to close the study prior to its expiration..
- 7. I will report to the HSC any unanticipated problems involving risk to participants.
- 8. I am in compliance with the requirements set by the University and qualify to serve as the principal investigator of this project or I have a faculty advisor.

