3. **Research Plan:** Summarize the study design and research procedures using non-technical language that can be readily understood by someone outside the discipline. If working with a Non-Government Organization (NGO) or other organization, be sure to highlight which are research-only activities and which activities would occur regardless of the research.

We propose to test the efficacy of an online CBT intervention (EQuIP) that addresses the pathways through which minority stress compromises LGBTQ young adults' co-occurring mental (e.g., depression) and behavioral (e.g., substance use, condomless anal sex) health problems. In this RCT, we expand upon the initial success of our pilot trial of our in-person treatment delivered solely to young adult gay and bisexual men and lessons learned from our other ongoing RCTs of our in-person treatments with LGBTQ young adults to determine if the treatment is efficacious when delivered online and if its efficacy exceeds that of the self-monitoring control.

To conduct this test, 120 participants will be randomly assigned to one of two conditions:

- Self-monitoring control: In this control condition, participants will be asked to indicate their past 7-day mood; stress experiences; and mental and behavioral health on an online survey. This type of self-monitoring has been shown to yield improvement in behavioral health outcomes. Self-reporting LGBTQ stress experiences has also been shown to produce reductions in depression symptoms over time. Participants will record these experiences once per week for 10 weeks.
- 2) Online EQuIP: This online CBT treatment consists of 10 weekly modules that participants will complete over the course of 10 weeks. Modules contain weekly psychoeducational text and vignettes about minority stress and mental health; brief videos illustrating the CBT skills; and homework exercises that therapists review and provide feedback on. Homework exercises include weekly tracking of stressful situations and mood, practicing new skills (e.g., mindfulness, cognitive restructuring), and exercises related to considering the origins of stress and negative emotions that participants may be experiencing. Therapists provide feedback after each homework assignment, including reviewing each participant's treatment goals as part of the first session's homework. Therapists who support this condition will be instructed to incorporate LGBTQ-specific content and feedback into

Page 4 of 22

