After completing the baseline assessment, participants will be assigned a study therapist and will be contacted by their therapist to schedule a 30-minute introductory call via Zoom video conferencing or telephone. During this conversation, therapists will explain the structure of the study and briefly discuss the participant's motivations and goals for participating in the study. Participants will then complete one session (self-monitoring, online EQuIP, or enhanced online EQuIP) per week. If participants miss a session, as determined by daily therapist and RA review of session access and self-monitoring or homework completion, they will receive a reminder to complete the session. Participants will also be asked to schedule a check-in phone call with their study therapist two-weeks post-randomization to discuss their progress through the study sessions. Participants will have a window period of four months to complete all 10 sessions. At 8-month followup, 20 participants randomized to the Online EQuIP condition who completed the treatment will be contacted and invited to participate in a 45-60 minute phone interview. The purpose of this phone interview is to ask participants to answer questions in regard to their experience in completing the treatment (e.g., things they liked, things they did not like, things they would change).

Before we randomize participants into the full trial, we will pilot-test the online EQuIP treatment with 14 LGBTQ young adults who meet all eligibility criteria planned to be employed for the full trial. In addition to completing 10 online EQuIP sessions, these participants will complete baseline and immediate post-treatment (3-month followup) assessments as well as a qualitative interview about their experience at 3-month followup. These participants will not complete any additional follow-up assessment.

4. **Participant Population:** Provide a detailed description of the types of participants who will be recruited into this study.

Inclusion criteria. Eligible participants will meet the following criteria: (1) aged 16-25, (2) identify as lesbian, bisexual, gay, or another sexual minority identity (e.g., pansexual, demisexual) (3) pastweek symptoms of depression or anxiety using the Brief Symptom Inventory-4 cutoff of 2.5 on either the depression subscale or anxiety subscale; (4) weekly access to internet on a laptop, desktop,

Page 5 of 22

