4) Peer-recruitment and referrals by previous and current study participants. Participants in the study will be asked to distribute study recruitment materials to peers who may be interested in participating in the study. Participants will be reminded that staff will never disclose any information about an individual's participation in the study, but that participants are free to disclose information about their own participation to whomever they desire. Participants are not required to distribute recruitment materials as a condition of study participation and the strictly voluntary nature of this request will be emphasized by study staff.

Recruitment text and images are attached to this application.

Are you collecting any information about the individuals prior to their signing a consent form? Yes \square No \boxtimes

If yes, indicate what information you will be collecting and how it will be gathered *(phone screen, paper questionnaire, etc.)*

2. **Indicate recruitment methods below.** Attach copies of any recruitment materials that will be used.

\boxtimes	Flyers	🛛 In	ternet/Web Postings	Radio
	Posters	$\boxtimes M$	ass E-mail Solicitation	🛛 Telephone
_	Letter		epartmental/Center Website	Television
imes	Newspaper			
\boxtimes	Through local NGO or other local conta	act	Social Media (Facebook, Twitter	ſ)
	Classroom recruitment			
	Table set-up / in-person recruitment of	public		
imes	Snowball sampling			
	Other (describe):			

3. Targeted Enrollment: Give the number of participants:

- a. Targeted for enrollment for this protocol: 120 (plus an additional 14 participants who will pilot the study)
- b. If this is a multi-site study, give the total number of participants targeted across all sites: N/A

4. How was this estimate derived?

We aim to recruit 120 participants into this study. Our primary aim is to demonstrate a greater reduction in 4-month follow-up in depressive symptoms in the online EQuiP condition compared to the self-monitoring control. Using a 1:1 randomization, we will randomly assign 60 participants to each of the two conditions (i.e., online EQuIP and the self-monitoring control). Assigning 60 participants into each condition will allow us to detect a difference ($\beta = 0.2, p < .05$) consistent with the average effect of online CBT involving therapist support (compared to a weak control condition) found across meta-analyses of online CBT: .61 (Andersson & Cuijpers, 2009), .83

Page 8 of 22

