Statistical Analysis Plan

A Trial of Online LGBTQ-affirmative Cognitive Behavioral Therapy to Reduce Depression and Associated Health Risks Among Young Adults
NCT04408469

01/18/2023

Intervention efficacy will be assessed using an intent-to-treat analysis and include all participants (n = 120). First, dependent variables and stigma moderators will be assessed for normality using skewness thresholds of ≥ 2 and kurtosis thresholds of ≥ 7 . If scales violate assumptions of normality, they will be square root transformed.

To examine the efficacy of LGBTQ-affirmative ICBT, we will use linear mixed models with maximum likelihood estimation and an unstructured covariance matrix to test the Condition × Time interaction effects between conditions over time for all continuous mental health outcomes (BSI, CESD, ODSIS, OASIS). For binary outcomes (suicidal thoughts, problematic drinking, SIDAS, sex-risk behavior), we will test intervention efficacy using a generalized linear mixed model with a logit link and a binomial distribution to test the Condition × Time effect predicting odds of each binary outcome between conditions over time. Primary efficacy analyses between conditions will include baseline (time = 0), immediate post-intervention (time =1), and 4-month follow-up (time = 2) to model the Condition × Time effect of receiving LGBTQ-affirmative ICBT (condition = 1) versus self-monitoring (condition = 0). Effect sizes (Cohen's d) for linear mixed models will be calculated as mean pre-post change (e.g., pre-intervention to post-intervention, pre-intervention to 4-month follow-up) in the LGBTQ-affirmative ICBT intervention minus the pre-post change in the self-monitoring condition, divided by the pooled baseline standard deviation.

To examine whether Condition × Time effects varied as a function of baseline levels of heterosexist stigma (i.e., internalized stigma, interpersonal stigma, and structural stigma), we will conduct moderation analyses using linear mixed models with maximum likelihood estimation, unstructured covariance matrix, and three-way interactions of Condition × Time × Stigma.

Moderation by internalized, interpersonal, and structural stigma will be entered together into

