multivariable models for each outcome. Significant three-way interactions of Condition \times Time \times Stigma will be further probed and plotted to contrast high stigma (one standard deviation above the mean) with low stigma (one standard deviation below the mean). All results will be evaluated at p < .05.

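### Neither the analysis nor the sample size allows for shared therapists, so if therapists affect outcomes materially more in EQuIP than in control, the Condition × Time standard errors are too small

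*Protocol*

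**What the plan says.** Protocol, 3. Research Plan, describes EQuIP as ten weekly modules with homework, and states that "Therapists provide feedback after each homework assignment". The control condition is a weekly online survey for ten weeks, with no therapist feedback described.

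The same section says that after baseline "participants will be assigned a study therapist and will be contacted by their therapist to schedule a 30-minute introductory call". That sentence is not limited to EQuIP. The two-week check-in call and the daily review of session completion by therapists and research assistants also read as applying to everyone. The protocol does not say how many therapists there are, how participants are allocated to them, or whether the same therapists serve both arms.

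Protocol, Section V, item 4 (How was this estimate derived?) says: "Assigning 60 participants into each condition will allow us to detect a difference" consistent with the "average effect of online CBT involving therapist support (compared to a weak control condition") from meta-analyses, citing .61, .83 and 1.00. It allows for 25% attrition and gives no ICC, design effect or therapist count.

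The SAP specifies "linear mixed models with maximum likelihood estimation and an unstructured covariance matrix" for continuous outcomes and a logit-link mixed model for binary outcomes. Neither has a therapist term, and no cluster-robust error or therapist-level sensitivity analysis is named. "All results will be evaluated at p < .05".

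**The concern.** Participants who receive ten rounds of feedback from the same therapist may end up more alike than participants of different therapists. The SAP's unstructured covariance, as described, covers the repeated measurements within one person. It does not cover correlation between people who share a therapist.

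If that correlation exists mainly in the EQuIP arm, the arm mean is less precise than the model assumes. The Condition × Time test would then reject a true null too often, its intervals would be too narrow, and a test with correct error control would have less power than planned. The protocol itself takes its expected effect from therapist-supported treatment, so a therapist contribution is plausible on its own terms.

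**Working it through.** **Inputs from the documents.** Two-group comparison, 60 per arm, 25% attrition (45 analysed per arm), p < .05, beta = 0.2 read as 80% power, smallest cited effect d = .61. The test is taken as two-sided, because that reproduces the stated size.

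**Assumptions, not in the documents.** k = 4 to 10 therapists in EQuIP; ICC = .02 to .10, with .01 added for power; equal caseloads m = 45/k.

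**1. The plan's own figure.** n = 2 × ((1.960 + 0.842)/0.61)² = 42.2, so 43 per arm; 43/0.75 = 57.3, so 58. The t-based version gives 44, then 59. Both are close to 60. No design effect is needed to reach the stated number. Power with 45 per arm: SE = √(2/45) = 0.2108; 0.61/0.2108 − 1.96 = 0.93; power 82.5%.

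**2. Clustering in EQuIP only.** DE = 1 + (m − 1) × ICC. True SE = √((DE + 1)/45). The ratio of true to assumed SE is r = √((DE + 1)/2). Type I error = 2 × (1 − Φ(1.96/r)). Power of a valid test = Φ(d/SE − 1.96).

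Example, k = 6, ICC .05: m = 7.5; DE = 1 + 6.5 × .05 = 1.325; r = √(2.325/2) = 1.078; type I error 6.9%. SE = √(2.325/45) = 0.2273; power = Φ(2.684 − 1.96) = 76.5%.

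| k | ICC | r | Type I error | Power at .61 | Power at .83 |
|---|---|---|---|---|---|
| 4 | .01 | 1.025 | 5.6% | 80.6% | 97.0% |
| 4 | .05 | 1.121 | 8.0% | 73.3% | 94.0% |
| 4 | .10 | 1.230 | 11.1% | 65.3% | 89.3% |
| 6 | .01 | 1.016 | 5.4% | 81.3% | 97.2% |
| 6 | .05 | 1.078 | 6.9% | 76.5% | 95.5% |
| 6 | .10 | 1.151 | 8.9% | 71.0% | 92.8% |
| 10 | .01 | 1.009 | 5.2% | 81.8% | 97.4% |
| 10 | .05 | 1.043 | 6.0% | 79.2% | 96.5% |
| 10 | .10 | 1.084 | 7.1% | 76.1% | 95.3% |

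Simulation of a simple t-test and a change-score test over k = 4 to 10 and ICC .02 to .10 gave about 5.3% to 11.7% type I error.

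**3. Break-even ICC for 80% power at .61.** DE = 45 × (0.61/2.802)² − 1 = 1.133, so ICC = 0.133/(m − 1): 0.133/10.25 = .013 (k = 4), 0.133/6.5 = .021 (k = 6), 0.133/3.5 = .038 (k = 10). For 3 to 12 therapists and ICC up to .10, power is at least 85% at .83 and at least 95% at 1.00.

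**4. Same therapists in both arms.** Let c be the size of the therapist effect in control relative to EQuIP, with the same therapists and total variance 1 in each arm. The variance ratio is r² = [2 − ICC(1 + c²) + m(1 − c)²ICC]/2.

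- c = 0 returns step 2.
- c = 0.5, k = 4, ICC .10: [2 − .125 + .281]/2 = 1.078, type I error 5.9%.
- c = 1: r² = 1 − ICC, so at ICC .10 type I error is 3.9%.

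Simulation agrees: about 4.4% to 6.2% across the grid at c = 0.5, and about 3.8% to 5.3% at c = 1. Setting r² = 1 gives c = [m − √(2m − 1)]/(m − 1), which is .65 (k = 4), .58 (k = 6) or .48 (k = 10). Above that relative control effect, the planned test is no longer anti-conservative.

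**Limits.** These are two-group approximations. Neither the three-occasion Condition × Time model nor the logistic models were simulated. The normal approximation ignores the few degrees of freedom that go with few therapists, which understates the power loss. It also ignores any precision gained from baseline and repeated measures.

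**The case against.** The strongest reply is that the direction of the error depends on a design fact the documents leave open. Participants in general are assigned a therapist, so the same therapists may serve both arms. With equal influence in both arms the therapist effect cancels and the planned test is slightly conservative. This stands. A reader might infer that the SAP model is anti-conservative for any positive therapist effect, or that its standard errors are certainly too small and 80% power certainly overstated. The documents support neither. Crossing removes the problem only when influence is fairly similar in the two arms, however, and that is hard to square with ten rounds of feedback in one arm against two calls and completion monitoring in the other.

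On power, the protocol ties its 80% to no single cited effect. Only .61 is vulnerable, although it is the value that reproduces 60 per arm, and even there power stays at 80% or more at ICC .01 with 4 to 10 therapists. The loss also applies to a valid test; the uncorrected test keeps most of its rejection rate because its error rate is inflated.

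On timing, the protocol's payments section expects the last follow-up in February 2022 and the SAP is dated 01/18/2023, so restating power cannot change the trial.

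Replacing the primary model is also debatable. The therapist count is unknown, a random effect limited to EQuIP would be misspecified if therapists are crossed with arm, and with zero therapist variance a nested model would have power of about .72 to .79 instead of .82.

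**Conclusion.** The concern holds conditionally. Neither the analysis nor the sample size allows for participants sharing a therapist, and the described contact differs sharply between arms. If therapist effects are materially larger in EQuIP than in control, the planned standard errors are too small. With no influence on controls, the likely damage runs from negligible (10 therapists, ICC .02) to roughly double the nominal error rate (4 therapists, ICC .10). With half the influence on controls it is about one percentage point at most. Power is a concern only at the smallest cited effect. All of these sizes rest on assumed therapist counts and ICCs. The unknowns are a reason to report and test the therapist effect; they do not justify treating it as zero, and they do not justify discarding the SAP model.

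**What to change.** Keep the SAP models and specify beside them a therapist-level analysis of both the linear and the logistic outcomes:

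- If therapists serve EQuIP only, use a partially nested model with a therapist random effect in that arm.
- If they serve both arms, use therapists crossed with condition, with a therapist-by-condition term so that the therapist variance can differ by arm.
- Use small-sample degrees of freedom for the linear models.
- Report the number of therapists, their allocation by arm and the therapist ICC.
- Qualify the efficacy conclusion if the two analyses disagree.

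If power is restated, give it as a range over ICC and therapist count, labelled as assumptions.

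The cost is SAP wording and one additional analysis, using assignments the trial already makes. The intervals will be wider, and with few therapists the therapist variance will be imprecisely estimated, which is why this analysis belongs beside the SAP model and not in its place.
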